The signed pathology report will be monitored by the responsible clinical research associate and kept with the subject's source documents onsite. Subjects should not be enrolled if high grade colonic dysplasia or colon cancer is discovered at the Screening endoscopy. Subjects may be enrolled if low grade colonic dysplasia is discovered during endoscopy and is completely removed. If a diagnosis of high grade colonic dysplasia or colon cancer is discovered during any subsequent endoscopic evaluation during the course of the study, the findings should be recorded as an AE and the subject should be discontinued from the study. If low grade colonic dysplasia is discovered during any subsequent endoscopic evaluation during the course of the study, the findings should be entered as an AE and the subject can continue in the study if the lesion has been completely removed.

During all endoscopies up to 3 sets of biopsies are to be collected; one mandatory set of biopsies and, if consented for, two optional sets of biopsies. Each set of biopsies should consist of 2 samples each, obtained from the rectosigmoid colon (approximately 15 –

30 cm from the anal verge) for histologic assessment. For each set of 2 samples, one should be taken from the area of most inflammation (if the area is ulcerated, the sample should be obtained from the edge of the ulcer), and one from an area that is representative of the general degree of mucosal inflammation present in that segment. For all histology biopsies, the location of the biopsy specimen (distance from the anal margin) should be recorded.

For China only: only a single biopsy at each endoscopy from the most inflamed area (HistoMOST) will be required per local requirements. The single, required biopsy will be taken from the area of most inflammation (if the area is ulcerated, the sample should be obtained from the edge of the ulcer) for histologic assessment at each required timepoint as per [Appendix C](#).

For follow-up endoscopies, in the absence of any visible lesions or areas of general inflammation characteristic of UC, up to 3 sets of biopsies should be collected from normal mucosa in the same segments as noted above.

Biopsy Sample Collection, Storage and Shipping:

Biopsies performed to confirm the diagnosis of UC or to rule out current dysplasia/malignancy should be processed and read locally per site standards.

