Biopsy specimens per subject should be obtained by endoscopy for histologic assessment at the time points indicated in [Appendix C](#) and [Appendix E](#). Using routine forceps for tissue collection, obtain the required number of biopsy specimens and process the specimens following the instructions in the study-specific laboratory manual.

Intestinal Tissue Analysis

The following analyses will be sent to the central laboratory and performed on tissue samples:

1. Qualitative UC histological assessment using Geboes histologic activity score,²⁵ and other histologic scoring systems. These samples may not be read in real time, however if unexpected findings, such as dysplasia, are noted on the histology biopsies, the central laboratory will contact the investigator to inform him/her about the unexpected finding. Subjects who are found to have high grade colonic dysplasia on the submitted biopsy will be terminated from the trial at the time the dysplasia is discovered. Unexpected findings should be recorded as an adverse event.
2. Subjects will have the option to provide tissue biopsies (per local requirements) for future exploratory research and/or validation studies. For more information, please refer to Section 5.3.1.2.

COVID-19 Pandemic-Related Acceptable Protocol Modifications

Biopsy completion should follow the endoscopy guidance if the visit is affected by COVID-19. If an endoscopy is completed at an alternative location from the study site the study required biopsy is not required. Biopsy can be completed per endoscopist's discretion for local evaluation.

Follow-Up Period

Subjects will be contacted approximately 30 days after the last administration of study drug to obtain information on any new or ongoing adverse events (AEs).

During this follow-up call the results of the follow-up at home pregnancy test should be communicated to the site and follow reporting found in Section 6.1.6.

Subjects may discontinue study drug treatment at any time during study participation. Subjects that end study participation early will have a Premature Discontinuation Visit and complete the procedures outlined for the PD Visit in [Appendix C](#) through [Appendix F](#) as soon as possible after the last dose of study drug and preferably prior to the administration of any new therapies.

Unscheduled Visits

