5.4 Removal of Subjects from Therapy or Assessment

5.4.1 Discontinuation of Individual Subjects

A subject may withdraw from the study at any time. The investigator may discontinue any subject's participation for any reason, including an adverse event, safety concerns or failure to comply with the protocol. Toxicity management criteria for events of serious infections, malignancy, cardiovascular events, gastrointestinal perforation, ECG abnormality, and select laboratory abnormalities are described in Section 6.1.7 Toxicity Management.

Subjects must have study drug discontinued immediately if any of the following occur:

- Clinically significant abnormal laboratory results or adverse events, which rule out continuation of the study medication, as determined by the investigator and the AbbVie TA MD.
- The investigator believes it is in the best interest of the subject.

- The subject requests withdrawal from study drug or the study.
- Inclusion and exclusion criteria violation was noted after the subject started study drug, when continuation of the study drug would place the subject at risk as determined by the AbbVie TA MD.
- Introduction of prohibited medications or dosages when continuation of the study drug would place the subject at risk as determined by the AbbVie TA MD.
- Subject is non-compliant with TB prophylaxis (if applicable) or develops active TB at any time during the study.
- The subject becomes pregnant while on study medication.
- Subject is significantly non-compliant with study procedures which would put the subject at risk for continued participation in the trial as determined by investigator or the AbbVie TA MD.
- Serious infections (e.g., sepsis) which cannot be adequately controlled by anti-infective treatment or would put the subject at risk for continuation of the study drug.
- Malignancy, except for localized NMSC or carcinoma in-situ of the cervix
- Subject develops a gastrointestinal perforation (other than appendicitis or mechanical injury)
- Confirmed diagnosis of deep vein thrombosis, pulmonary embolus or non-cardiac, non-neurologic arterial thrombosis

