In order to minimize missing data for efficacy and safety assessments, subjects who prematurely discontinue study drug treatment should continue to be followed for all regularly scheduled visits as outlined in the Study Activities daily, unless they have decided to discontinue the study participation entirely (withdrawal of informed consent). Subjects should be advised on the continued scientific importance of their data even if they discontinue treatment with study drug early.

If a subject prematurely discontinues study participation (withdrawal of informed consent), the procedures outlined for the Premature Discontinuation Visit must be completed as soon as possible, preferably within 2 weeks.

A final telephone visit will occur for all subjects, approximately 30 days after the last dose of study medication to determine the status of any ongoing AEs/serious AEs (SAEs) or the occurrence of any new AEs/SAEs.

All attempts must be made to determine the date of the last study drug dose and the primary reason for premature discontinuation or study participation. The information will be recorded on the appropriate eCRF page. However, these procedures should not interfere with the initiation of any new treatments or therapeutic modalities that the investigator feels are necessary to treat the subject's condition. Following discontinuation of the study drug, the subject will be treated in accordance with the investigator's best clinical judgment, irrespective of whether the subject decides to continue participation in the study.

For subjects that are considered lost to follow-up, reasonable attempts must be made to obtain information on the final status of the subject. At a minimum, two phone calls must be attempted and one certified letter must be sent and documented in the subject's source documentation.

Subjects who discontinue the study prematurely will not be replaced.

COVID-19 Pandemic-Related Acceptable Protocol Modification

During the COVID-19 pandemic, it has been necessary to employ mitigation strategies to enable the investigator to ensure subject safety and continuity of care. Acceptable mitigation strategies are identified and included in Section 5.3.1.1 and [Appendix C](#) and [Appendix E](#).

The investigator should contact the sponsor medical contact before discontinuing a subject from the study for a reason other than "planned per protocol," to ensure all acceptable mitigation steps have been explored.

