Malignancy and Gastrointestinal (GI) Dysplasia: Subjects who develop malignancy other than nonmelanoma skin cancer (NMSC) or carcinoma in situ of the cervix, should be discontinued. Subjects who develop high grade colonic dysplasia, should be discontinued. Information including histopathological results should be queried for the confirmation of the diagnosis. Periodic skin examination is recommended for subjects who are at increased risk for skin cancer.

Thrombosis Events: Subjects who develop symptoms of thrombosis should be promptly evaluated and treated appropriately. If the diagnosis of deep vein thrombosis, pulmonary embolus or non-cardiac, non-neurologic arterial thrombosis is confirmed, the subject must be discontinued from study drug.

ECG Abnormality: Subjects must be discontinued from study drug for an ECG change considered clinically significant and with reasonable possibility of relationship to study drug.

Management of Select Laboratory Abnormalities: For any given laboratory abnormality, the investigator should assess the subject, apply the standard of care for medical evaluation and treatment and follow any local guidelines. Specific toxicity management guidelines for abnormal laboratory values are described in [Table 5](#), and may require a supplemental eCRF to be completed. All abnormal laboratory tests that are considered clinically significant by the investigator will be followed to a satisfactory resolution. If a repeat test is required per [Table 5](#), the repeat testing must occur as soon as possible.

Table 5. Toxicity Management Guidelines for Abnormal Lab Values

Hemoglobin	
 • If hemoglobin < 8.0 g/dL interrupt study drug dosing and confirm by repeat testing with new sample. • If hemoglobin decreases from Baseline ≥ 3.0 g/dL without an alternative etiology, interrupt study drug dosing and confirm by repeat testing with new sample. • If hemoglobin decreases ≥ 3.0 g/dL from Baseline and an alternative etiology is known or the hemoglobin value remains in the normal reference range, the subject may remain on study drug at the investigator's discretion. • If confirmed, continue to withhold study drug until hemoglobin value returns to normal reference range or its Baseline value.

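### Protocol 6.1.7 exempts all non-melanoma skin cancer from the malignancy stop rule, whereas 5.4.1 exempts only localized disease

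*Protocol*

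**What the plan says.** Protocol 5.4.1 opens its stop list with "Subjects must have study drug discontinued immediately if any of the following occur". One item on that list is "Malignancy, except for localized NMSC or carcinoma in-situ of the cervix". The same section tells the reader where the detailed criteria are: "Toxicity management criteria for events of serious infections, malignancy, cardiovascular events, gastrointestinal perforation, ECG abnormality, and select laboratory abnormalities are described in Section 6.1.7".

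The malignancy paragraph of Protocol 6.1.7 reads: "Subjects who develop malignancy other than nonmelanoma skin cancer (NMSC) or carcinoma in situ of the cervix, should be discontinued". It does not refer back to 5.4.1.

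Two neighbouring provisions matter only as notes:

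- **Colon cancer or high-grade dysplasia at a later endoscopy.** Protocol 5.3.1.1 (Biopsy During Endoscopy) says "the findings should be recorded as an AE and the subject should be discontinued from the study". The general follow-up rule in 5.4.1 is that "subjects who prematurely discontinue study drug treatment should continue to be followed for all regularly scheduled visits as outlined in the Study Activities", with withdrawal of consent as the stated exception.
- **High-grade dysplasia on central histology.** Protocol 5.3.1.1 (Intestinal Tissue Analysis) says "Subjects who are found to have high grade colonic dysplasia on the submitted biopsy will be terminated from the trial". Section 6.1.7 also calls for discontinuation. The 5.4.1 list has no dysplasia item.

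**The concern.** A safety stop should give one answer for one diagnosis. Here the answer for non-localized NMSC depends on which section the site reads, and the stricter section directs the site to the looser one. At stake is continued dosing of an immunomodulator in a subject whose cancer the stop list treats as a reason to end it.

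The topic is not peripheral. Malignancy of every type is an adverse event of special interest in Protocol 6.1.1.3, and NMSC has its own search category in Appendix B of the Substudy 3 SAP.

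There is also a record-keeping consequence. Protocol 7.0 makes it reportable when a subject meets withdrawal criteria and is not withdrawn, and Appendix A of the Substudy 3 SAP tabulates that category. The protocol does not define withdrawal criteria. If the 5.4.1 list supplies them, which is an assumption, a subject with non-localized NMSC who stays on drug is a deviation, even though a site reading only 6.1.7 would not see one.

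**Working it through.** The plan has no figure to reproduce on this point, so the check is a comparison of current protocol text.

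**1. The two rules by diagnosis**

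| Diagnosis | Protocol 5.4.1 | Protocol 6.1.7 |
|---|---|---|
| Localized NMSC | Exempt | Exempt |
| Cervical carcinoma in situ | Exempt | Exempt |
| Non-localized NMSC | Mandatory, immediate study-drug stop | Exempt |
| Any other malignancy | Mandatory, immediate study-drug stop | *Should* be discontinued; the sentence does not say from what |

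The scope differs in one row, non-localized NMSC. The force of the rule (*must* against *should*) differs for every other non-exempt malignancy.

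**2. Direction of the cross-reference.** 5.4.1 names malignancy among the events whose criteria are in 6.1.7. A site following that pointer arrives at the weaker wording and finds no pointer back.

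**3. Neighbouring rules in 6.1.7.** Active tuberculosis, gastrointestinal perforation, confirmed thrombosis and a clinically significant drug-related ECG change all carry *must* and all specify discontinuation from study drug. The first three match their items in the 5.4.1 list. The malignancy sentence departs from that pattern in force, and from 5.4.1 in scope. This looks like a drafting slip and not a deliberate relaxation.

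**4. Whether the rule still operates.** Substudy 3 enrolment is closed (Protocol Synopsis), but Protocol 8.1 keeps subjects who are unfinished at database lock on blinded treatment until they complete. The stop rule can therefore still be applied.

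**5. Size.** The number of non-localized NMSC cases cannot be derived from the documents. For efficacy, a ceiling per subject is enough. The Substudy 3 SAP (2.4) plans 150 subjects per arm, with remission rates of 12% and 40%.

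- Planned difference: 40 − 12 = 28 percentage points.
- Largest shift from one subject: 1/150 = 0.67 percentage points.
- Ratio: 0.67/28 = 2.4% of the planned difference.

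**The case against.** The strongest reply is that 6.1.7 never says a subject with NMSC may stay on drug. It limits whom it tells sites to discontinue and is silent on the rest. The 5.4.1 list is independent and mandatory, so keeping a subject with non-localized NMSC on drug breaches the protocol whatever 6.1.7 says. Obeying 5.4.1 breaches nothing in 6.1.7. The list also requires a stop when "The investigator believes it is in the best interest of the subject".

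All of that is correct, and it keeps the point minor. It does not remove the point, because 5.4.1 itself names 6.1.7 as the home of the malignancy criteria. A site is entitled to read the exemption there as the detailed version of the rule.

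A reader might also infer two stronger defects. The documents support neither.

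- **A flat contradiction on colon cancer**, with study exit in 5.3.1.1 against continued visits in 5.4.1. The wording does differ. However, 5.4.1 also lets the investigator end any subject's participation for any reason, including an adverse event. Its continued-visits rule is a *should* default, stated as a way to limit missing data. The 5.3.1.1 instruction can be read as the specific rule within that default. Dosing ends under either reading.
- **A missing safeguard for high-grade dysplasia**, because the 5.4.1 list omits it. Both passages in 5.3.1.1 and the one in 6.1.7 already discontinue these subjects, and the introduction to 6.1.7 describes its action as discontinuation from study drug. 5.3.1.1 also records dysplasia as an adverse event, so the 5.4.1 item on adverse events that rule out continued treatment can cover it. This is an omission from one list.

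**Conclusion.** The inconsistency on NMSC is real and is wrong as written: an operative safety rule has a narrower exemption in 5.4.1 than in the section 5.4.1 points to. Severity is minor.

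This rests on two judgements that the documents do not settle. First, very few subjects will develop non-localized NMSC. Second, some sites will act on 6.1.7 without returning to 5.4.1. The possible deviation consequence further assumes that the 5.4.1 list is what Protocol 7.0 means by withdrawal criteria.

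With so few subjects, each able to move an arm by at most 0.67 points, the efficacy conclusion is unaffected. Nothing here shows that any subject was harmed or wrongly kept on drug. The colon cancer and dysplasia wording deserves a note only.

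**What to change.** In the malignancy sentence of Protocol 6.1.7:

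- put *localized* before NMSC;
- replace *should be discontinued* with *must be discontinued from study drug*;
- add a reference to Section 5.4.1.

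This adopts the stricter rule the protocol already contains.

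Optional tidying at the same time:

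- Add a cross-reference between the 5.3.1.1 endoscopy rule and the 5.4.1 follow-up rule, stating which governs colon cancer. Study exit or continued visits is the sponsor's choice.
- Add high-grade dysplasia to the 5.4.1 list for consistency.

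The cost is a few words and no new procedures. Under Protocol 9.1 an amendment goes to the ethics committee or review board, so the change is best carried in the next amendment and not issued alone.

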- e. During Screening, biologic drug levels may be optionally assessed at the investigator's discretion as an alternative to completing the required washout period: (1) infliximab and natalizumab: may be tested approximately 4 weeks or later from the last dose; (2) adalimumab, certolizumab, golimumab, or vedolizumab: may be tested approximately 6 weeks or later from the last dose; (3) ustekinumab: may be tested approximately 8 weeks or later from the last dose.

COVID-19 Pandemic-Related Acceptable Protocol Modifications

If travel restrictions or other changes in local regulations in light of the COVID-19 pandemic prevent the subject from having blood drawn for laboratory testing at the study site, if possible, arrange for subjects to have laboratory work done at a local lab, hospital, or other facility. It is recommended to perform all scheduled tests in the protocol, except for hs-CRP, Fecal calprotectin, PK, and optional samples for exploratory research which should not be collected. For hs-CRP local testing can only be performed if deemed to be necessary by the investigator after discussion with TA MD.

Local lab results should be obtained along with reference ranges and kept within the subjects' source documentation. The results should be reviewed by the investigator and documented in EDC as an unscheduled lab as soon as possible.

If it is not possible to perform all the tests, the tests in the below table should be performed at minimum for safety evaluation.

Hematology	Clinical Chemistry	Urine	Tuberculosis tests*
Hematocrit Hemoglobin RBC count WBC count Neutrophils Bands Lymphocytes Monocytes Basophils Eosinophils Platelet count	BUN Creatinine Total bilirubin ALT AST Alkaline phosphatase CPK	Pregnancy test	QuantiFERON TB test or PPD (Study M14-234 SS3 and Study M14-533) Chest X-Ray (Study M14-234 SS3 and Study M14-533)

* TB Test and Chest X-Rays to be completed only at the required visits per protocol.

If laboratory samples cannot be obtained, study drug administration may be continued provided that the following criteria are met:

During Substudy 2 drug may be dispensed if:

1. There is at least 1 post-Baseline lab assessment (either Week 2 or Week 4 visit)
AND
2. The investigator has reviewed all prior laboratory results and confirms and discusses with the subject via a phone/video call that there is no safety concern for the subject to continue use of the study drug in the absence of current labs
AND

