Absolute neutrophil count (ANC)	
 • If confirmed < 1000 cells/μL by repeat testing with new sample, interrupt study drug dosing until ANC value returns to normal reference range or its Baseline value. • Interrupt study drug if confirmed < 500/μL by repeat testing with new sample. If value returns to normal reference range or its Baseline value, restarting study drug is allowed if there is an alternative etiology identified; documentation should include reason that rechallenge is expected to be safe for the subject. Study drug should be discontinued if no alternative etiology can be found.
Absolute lymphocyte count (ALC)	
 • If confirmed < 500 cells/μL by repeat testing with new sample, interrupt study drug dosing until ALC returns to normal reference range or its Baseline value.
Total white blood cell count	
 • If confirmed < 2000 cells/μL by repeat testing with new sample, interrupt study drug dosing until white blood cell count returns to normal reference range or its Baseline value.
Platelet count	
 • If confirmed < 50,000 cells/μL by repeat testing with new sample, interrupt study drug dosing until platelet count returns to normal reference range or its Baseline value.

Table 5. Toxicity Management Guidelines for Abnormal Lab Values (Continued)

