AST or ALT	
 • Interrupt study drug immediately if confirmed ALT or AST $> 3 \times$ ULN by repeat testing with new sample and either a total bilirubin $> 2 \times$ ULN or an international normalized ratio (INR) > 1.5. 
 ○ A separate blood sample for INR testing will be needed to measure INR at the time of repeat testing for ALT or AST. A repeat test of INR is not needed for determination if above toxicity management criteria are met. • Interrupt study drug immediately if confirmed ALT or AST $> 3 \times$ ULN by repeat testing with new sample along with appearance of fatigue, nausea, vomiting, right upper quadrant pain or tenderness, fever, rash, and/or eosinophilia ($> 5\%$). • Interrupt study drug immediately if confirmed ALT or AST $> 5 \times$ ULN by repeat testing with new sample for more than 2 weeks. • Interrupt study drug immediately if confirmed ALT or AST $> 8 \times$ ULN by repeat testing with new sample. • Subjects with HBc Ab+ (irrespective of HBs Ab status) and negative HBV DNA PCR testing at screening who develop the following should have HBV DNA by PCR testing performed within 1 week (based on initial elevated value): 
 ○ ALT $> 5 \times$ ULN OR ○ ALT or AST $> 3 \times$ ULN if an alternative cause is not readily identified. 
 • A separate blood sample for HBV DNA PCR testing will be needed at the time of repeat testing for ALT or AST. 
A positive result for HBV DNA PCR testing in these subjects will require immediate interruption of study drug (unless not acceptable by local practices) and a hepatologist consultation should occur within one week for recommendation regarding subsequent treatment.
 
Subjects who meet any of the above criteria should be evaluated for an alternative etiology of the ALT or AST elevation and managed as medically appropriate. If applicable, the alternative etiology should be documented in the eCRF. If ALT or AST values return to the normal reference range or its Baseline value, study drug may be restarted. If restarting study drug, documentation should include reason that rechallenge is expected to be safe. If after clinically appropriate evaluation, no alternative etiology for ALT or AST elevation is found or the ALT or AST elevation has not resolved or is not trending down toward normal, the subject should be discontinued from study drug.
 
For any confirmed ALT or AST elevations > 3 ULN, complete supplemental hepatic eCRF

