------------	---

Table 5. Toxicity Management Guidelines for Abnormal Lab Values (Continued)

Serum Creatinine (sCr)	
If serum creatinine is $> 1.5 \times$ the Baseline value and $> \text{ULN}$, repeat the test for serum creatinine (with subject in an euvoletic state) to confirm the results. If the results of the repeat testing still meet this criterion then interrupt study drug and restart study drug once serum creatinine returns to $\leq 1.5 \times$ Baseline value and $\leq \text{ULN}$. 
For the above serum creatinine elevation scenario, complete supplemental renal eCRF(s).

Creatine Phosphokinase	
If confirmed CPK value $> 4 \times \text{ULN}$ and there are no symptoms suggestive of myositis or rhabdomyolysis, the subject may continue study drug at the investigator's discretion.If CPK $> 4 \times \text{ULN}$ accompanied by symptoms suggestive of myositis or rhabdomyolysis, interrupt study drug and contact AbbVie TA MD.For above CPK elevation scenarios, complete supplemental CPK eCRF.

If the subject must undergo elective surgery, the study drug should be interrupted 1 week prior to the surgery. If the subject must undergo emergency surgery, the study drug should be interrupted at the time of the surgery. The study drug can recommence once the physician has examined the surgical site and determined that it has healed and there is no sign of infection.

Repeat testing must be performed by central laboratory.

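### Table 5 requires central-laboratory confirmation before interruption for six parameters, but the COVID-19 provisions allow local testing without saying whether a local repeat confirms; separately, two hemoglobin bullets overlap with no stated precedence

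*Protocol*

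**What the plan says.** **Confirmation.** In Protocol 6.1.7, Table 5, a low ANC must be confirmed "by repeat testing with new sample, interrupt study drug dosing until ANC value returns to normal reference range or its Baseline value". The ALC row has the same form ("interrupt study drug dosing until ALC returns to normal reference range or its Baseline value"), as do total WBC and platelets. All four AST/ALT enzyme thresholds call for a confirmed value; one requires the elevation to be confirmed "by repeat testing with new sample for more than 2 weeks". For creatinine: "If the results of the repeat testing still meet this criterion then interrupt study drug". The text before the table asks for repeats as soon as possible. The text after it says "Repeat testing must be performed by central laboratory".

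**COVID-19 provisions.** Where the pandemic prevents a blood draw at the site, Protocol 5.3.1.1 (Clinical Laboratory Tests) tells sites, if possible, to "arrange for subjects to have laboratory work done at a local lab, hospital, or other facility". Local results go to the investigator for review and into EDC as unscheduled laboratory data. Section 9.2 lists a local in place of a central laboratory among the acceptable alternative measures. Appendices C and E mark chemistry and hematology as activities that a local centre may perform.

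**Hemoglobin.** The first bullet of that Table 5 row reads "If hemoglobin < 8.0 g/dL interrupt study drug dosing and confirm by repeat testing with new sample". The third covers a fall of at least 3.0 g/dL from Baseline and leaves the decision to the investigator: "an alternative etiology is known or the hemoglobin value remains in the normal reference range, the subject may remain on study drug".

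**The concern.** Table 5 exists so that all sites act on the same laboratory thresholds. For six parameters its mandatory action needs a central repeat, while the pandemic text allows testing by another route and does not connect the two. A site holding two abnormal local values cannot tell from the protocol whether the rule has been triggered. Sites may then act differently, which bears on subject safety and on the comparability of recorded interruptions.

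The Substudy 3 SAP, section 9.3, uses central and local laboratory data in its analyses. A local Grade 3 or 4 value that has worsened from baseline would therefore be tabulated as potentially clinically significant, although a local repeat may not confirm it for Table 5.

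The hemoglobin row raises a different problem. One subject can meet a bullet that requires interruption and a bullet that permits continuation.

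**Working it through.** No sample size, power or alpha figure lies behind this point, so there is no stated figure to reproduce. The check compares the rules and then does short arithmetic on hemoglobin.

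**Part 1: confirmation**

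1. Table 5 rules by what triggers interruption:
   - A confirmed repeat is needed for ANC, ALC, total WBC, platelets, AST/ALT and creatinine: six parameters.
   - No prior confirmation is needed for hemoglobin below 8.0 g/dL, a hemoglobin fall of at least 3.0 g/dL without an alternative etiology, CPK above 4 × ULN with symptoms, or a positive HBV DNA test.
2. Where the repeat is run: the central laboratory (end of 6.1.7), with no pandemic exception.
3. What may be tested locally: the minimum safety panel in 5.3.1.1 includes neutrophils, lymphocytes, WBC, platelets, ALT, AST and creatinine. That covers all six parameters.
4. Text joining the two: none found. Section 5.3.1.1 asks for investigator review and data entry of local results but does not mention Table 5 confirmation. Elsewhere the protocol does settle such questions: HBV DNA PCR may be completed by a local laboratory under COVID-19 restrictions, and an indeterminate QuantiFERON result is repeated locally first.
5. Consequence: take a subject who cannot be drawn at the site and whose ANC is below 1000 cells/µL on a local test and again on a local repeat. Under the literal text of 6.1.7 the value may not be confirmed, so the mandatory interruption may not apply.

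**Part 2: hemoglobin**

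Let *b* be the Baseline value and *v* the current value in g/dL, with an alternative etiology known.

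- Bullet 1 (interrupt): *v* < 8.0.
- Bullet 3 (may remain): *b* − *v* ≥ 3.0, that is *v* ≤ *b* − 3.0.
- Both apply when *v* < 8.0 and *v* ≤ *b* − 3.0.

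Results:

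- *b* = 9.0, the lowest value that passes screening (exclusion criterion 31 excludes values below 9): *v* ≤ 6.0 meets both, since 9.0 − 6.0 = 3.0 and 6.0 < 8.0.
- *b* below 11.0: *b* − 3.0 is below 8.0, so every fall of at least 3.0 also meets bullet 1.
- *b* of 11.0 or more: every value below 8.0 is a fall of more than 3.0. For example, 11.0 − 7.9 = 3.1.

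The overlap therefore exists at every admissible baseline. It does not depend on the laboratory's normal range, because a known etiology alone opens bullet 3.

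A side observation, on which the conclusion does not rest: bullets 2 and 3 also meet when a fall of at least 3.0 has no alternative etiology but the value stays in the normal range. That needs *b* of at least the lower limit of normal plus 3.0. The documents give no such limit; assuming 11.5 to 13.5 g/dL, the overlap starts at baselines of 14.5 to 16.5 g/dL.

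**The case against.** The strongest reply is that no subject is left without protection. Local results must be reviewed by the investigator (5.3.1.1). Section 6.1.7 asks for assessment and standard of care for any laboratory abnormality. Section 5.4.1 lets the investigator interrupt drug at any time, and requires stopping for clinically significant results that the investigator and the sponsor's medical director judge to rule out continuation; neither provision is limited to central results. Section 9.2 could be read as general permission to use a local laboratory. Home visits may include collection of laboratory tests, which might allow a central repeat, although the text does not say who analyzes those samples.

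Most of this stands, and it limits the point. A reader might infer that an abnormal local result could never lead to interruption; the safeguards above rule that out. They rest on judgment, however, whereas Table 5 sets uniform thresholds. Section 9.2 does not mention confirmation.

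A reader might also cite the 12-week limit for dispensing in Substudy 3 as the size of the gap. That rule applies when no laboratory samples can be obtained, not when a subject has been tested locally, and it carries its own investigator review. Nor does the request for prompt repeats contradict the central-laboratory rule, since a prompt central repeat satisfies both. The local route is also conditional, so the protocol does not send all affected subjects to local laboratories.

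On hemoglobin, bullet 1 is mandatory and bullet 3 permissive, so a site that interrupts complies with both. That is fair: the bullets are not two opposite commands. But no precedence is stated, and a site relying on bullet 3 can also point to the text.

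**Conclusion.** Two separate points hold.

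1. For six Table 5 parameters, the protocol does not say whether a local result or local repeat counts as confirmation under COVID-19 restrictions. Its literal wording suggests that it does not. What may fail is the mandatory trigger; investigator discretion remains.
2. Hemoglobin bullets 1 and 3 overlap at every admissible baseline when an alternative etiology is known, with no order of precedence. This is not an instance of the first point, because the interrupt bullets in that row act on the first value.

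The conclusion assumes that the closing sentence of 6.1.7 governs the confirmatory repeats in Table 5, which is its natural reading, and that Baseline hemoglobin is not below the screening limit of 9 g/dL. The number of subjects affected cannot be derived from the documents. Substudies 1 and 2 have completed induction and Substudy 3 enrollment is closed, so the practical reach is the remaining Substudy 3 treatment. No view is taken on which clinical rule is right.

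**What to change.** Issue a protocol clarification or site letter for the remaining Substudy 3 subjects that:

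- reconciles the local-testing text (5.3.1.1, 9.2, Appendices C and E) with 6.1.7 and Table 5, saying whether a local result or local repeat counts as confirmation when COVID-19 restrictions apply;
- reconciles the hemoglobin bullets with each other, saying which takes precedence when more than one is met.

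The content of both rules is for the sponsor's medical team. The cost is a short text change and its distribution to sites; no analysis or sample size changes.
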